2.1.2 Immune Activation in Elite Controllers

A small subset of the HIV-infected population (<0.5 percent) are able to maintain stable CD4 T cell counts and suppressed HIV RNA below the limit of detection in the absence of ART for decades [16-18]. Now termed elite controllers (ECs), these individuals are thought to control HIV replication through protective class I HLA haplotypes [19-21] and strong HIV-specific CD8 T cell responses [22-24]. However, despite suppression of viral replication below the limits of detection, ECs have higher rates of immune activation as measured by soluble biomarkers of inflammation such as D-dimer, IL-6, CRP, and markers of monocyte activation including soluble (s) CD163 and TF (tissue factor) [25-28] compared to healthy controls. In some cases, ECs have been noted to have higher levels of immune activation than those observed in HIV-infected progressors on effective ART (D-dimer and sTF) [29] and may possibly be at increased risk for cardiovascular complications [27].

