3.4.2 Secondary Endpoints

- To evaluate changes in soluble biomarkers (sCD14, IL-6, D-dimer, hsCRP, sCD163, sTF as well as other relevant markers of inflammation and coagulation) in EC and ART <50 groups treated with ASA or ATV, independently within each group and arm and with groups combined, at 6, 9, and 12 months.
- To evaluate changes in T cell activation (measured by HLA-DR/CD38 co-expression), monocyte immune activation (measured by activated monocyte subsets expressing either CD14⁺⁺CD16⁺ and CD14^{var}CD16⁺ and markers of activation, CCR5 and TF, and migration, CCR2 and CX3CR1), at 6, 9, 12 months of study.
- To investigate differences in HLA type, which has been implicated as a mechanism of viremic control in ECs, between groups and treatment arms, as it relates to treatment response.
- Assess if a wash out period following 9 months of therapy results in biomarker and cellular activation changes after 3 months (Month 15).
- To compare changes of biomarkers and cellular markers between EC and ART <50 groups after adjusting for smoking, CD4 counts and age.
- To compare changes of biomarkers and cellular markers between ATV and ASA arms of each group and in both groups combined.
- To evaluate changes in plasma viral load, as measured by single copy assay in EC and ART <50 groups treated with ASA or ATV at baseline, 3 and 12 months.
- Assess toxicity profile of ASA versus ATV in the study population.
- Assess prevalent atherosclerotic disease in EC vs ART<50 by MR imaging of carotids.
- Assess changes in MR imaging of carotids after 9 months of statin or ASA in each group and both groups combined.
- Correlate MR vascular imaging with soluble and cellular biomarkers of inflammation.

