13.5 Efficacy Analysis

The primary endpoint will be set as a change in sCD14 after 9 months of treatment with ASA or ATV, in ECs and in Treated Progressors (ART <50) combined. Assuming 40 patients enroll in each treatment arm, with a mean sCD14 of 2.45 µg/mL and a standard deviation of 0.45 µg/mL, the study has 95% power to detect a reduction of 0.20 in sCD14 levels (See Section 13.2) after 9 months of treatment. The significance of paired differences within each group will be evaluated using two-sided nonparametric (one-sample signed rank) test. As discussed above, this power decreases to 74% when treatment arms are compared individually within each group (as a secondary endpoint, see below). Adjustment for differences in CD4, age and smoking status will be done in any between group (EC vs ART<50) comparisons.

Secondary endpoints, including group comparisons (ASA vs statin and EC vs ART<50) of changes in biomarkers and T cell activation, cardiovascular disease prevalence, and changes in plasma viremia will be evaluated using two-sided nonparametric (Wilcoxon rank-sum) tests. Exploratory analyses comparing paired differences of carotid IMT thickness at Month 0 and Month 12 within each group will be assessed by two-sided nonparametric (one-sample signed rank) tests. Associations between continuous variables (MR measurements and biomarkers and cellular activation markers) will be assessed using Spearman rank order correlation coefficients. Linear regression models will be used to control for factors such as age, smoking, and inflammatory biomarkers. For all evaluations, type I error will be set at 0.05.

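### Section 13.5 names neither HIV group nor treatment arm for the MR–biomarker associations; if EC and ART<50 are pooled, a group difference alone can produce or hide a correlation

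*Combined protocol and SAP*

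**What the plan says.** Section 3.4.2 lists as a secondary endpoint: "Correlate MR vascular imaging with soluble and cellular biomarkers of inflammation". Section 13.5 gives the method: "Associations between continuous variables (MR measurements and biomarkers and cellular activation markers) will be assessed using Spearman rank order correlation coefficients". The next sentence is "Linear regression models will be used to control for factors such as age, smoking, and inflammatory biomarkers", and the section closes with "For all evaluations, type I error will be set at 0.05".

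None of these sentences names an analysis population, a time point, HIV group or treatment arm. The regression's outcome and exposure are not defined.

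The neighbouring text is more specific. The MR-change endpoint in 3.4.2 reads "Assess changes in MR imaging of carotids after 9 months of statin or ASA in each group and both groups combined". The one adjustment that 13.5 ties to HIV group is limited to comparisons of the groups: "Adjustment for differences in CD4, age and smoking status will be done in any between group (EC vs ART<50) comparisons". Section 13.1 argues for combining the groups only for the primary endpoint, and section 6.3 randomises the two groups separately.

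**The concern.** The trial enrols two deliberately different populations. Section 2.1.2 reports that in some cases D-dimer and sTF are higher in elite controllers than in treated progressors. Whether carotid MR differs between the groups is itself a secondary endpoint. Where a marker and an MR measure both differ by group, a correlation over all subjects mixes the between-group difference with the within-group association, and only the latter answers the objective. At Month 12, treatment arm can act in the same way if the drugs shift both variables.

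There is a second, smaller issue. Inflammatory biomarkers are the variables to be associated with MR, yet they also appear among the regression factors. Adjusting one marker for others that carry the same information can remove much of the association being sought.

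At stake is how a named secondary objective is read. A significant coefficient might show only that the two groups differ, and a real one might be missed.

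**Working it through.** The documents give no sample size, power or effect size for this analysis, so there is no planned figure to reproduce. The check tests the mechanism and its size.

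**Inputs from the documents.** 40 EC and 40 ART<50 (section 3.3); two-sided tests at 0.05 (section 13.5). MR may be omitted where contraindicated (sections 4.5 and 7.1), so 80 is an upper limit.

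**Assumed inputs.** Normal data, and mean shifts between groups of dx (marker) and dy (MR) in within-group SD units.

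**Induced correlation.** With equal groups and no within-group correlation, the pooled Pearson correlation is

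r = (dx·dy/4) / √[(1 + dx²/4)(1 + dy²/4)].

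- 0.5 SD on both: 0.0625/1.0625 = 0.06
- 0.8 SD on both: 0.16/1.16 = 0.14
- 1.0 SD on both: 0.25/1.25 = 0.20
- dx or dy equal to zero: 0

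**False-positive rate.** 20,000 simulated trials per row. The stratified version correlates within-group ranks (77 df), which is equivalent to a group term.

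| Shift, marker/MR (SD) | Mean pooled Spearman r | Pooled | Stratified |
|---|---|---|---|
| 0/0 | 0.00 | 5.0% | 5.0% |
| 0.8/0 | 0.00 | 5.1% | 5.2% |
| 0.25/0.25 | 0.01 | 5.2% | 5.0% |
| 0.5/0.5 | 0.06 | 7.8% | 5.1% |
| 0.8/0.5 | 0.09 | 12.3% | 5.0% |
| 0.8/0.8 | 0.14 | 22.5% | 4.7% |
| 1.0/1.0 | 0.20 | 44.3% | 4.7% |

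A separate run of 40,000 trials with unequal shifts gave pooled rates of 5.8% at 0.5/0.25 and 7.7% at 1.0/0.25. The smaller of the two shifts limits the damage.

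**Masking.** With a true within-group r of 0.30 and opposite shifts of 0.8 SD, power is 14% pooled and 71% stratified. With no shifts it is 74% pooled and 72% stratified, so stratifying when it was not needed costs about two points.

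**Treatment arm.** The same algebra applies with arm in place of group. It was not simulated separately.

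**Mutual adjustment of markers.** Assume every marker correlates c = 0.35 with MR and the markers correlate m with each other. Adjusting for one other marker gives

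partial r = c(1 − m) / √[(1 − c²)(1 − m²)].

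- m = 0.5: 0.175/√(0.8775 × 0.75) = 0.22
- m = 0.7: 0.105/√(0.8775 × 0.51) = 0.16

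Fisher-z power at n = 80 is Φ(atanh(r)·√(n − 3 − q) − 1.96), where q is the number of other markers in the model. It is 89% unadjusted. With one other marker it is 48% (m = 0.5) or 28% (m = 0.7). With three it is 18% or 10%.

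**The case against.** The strongest reply is that this is under-specification and not a stated error. Most of that stands.

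- A reader might infer that the correlations are definitely run over all 80 subjects. The documents do not say so. Correlations within each group are equally compatible with the text, and MR can be missing.
- A reader might infer that a group term is ruled out. The regression list is introduced with such as, so it is open: group is unnamed, not excluded.
- A reader might take 44% as the expected error rate. It needs a full-SD difference on both variables. Section 2.1.2 gives no size for the marker difference, and the MR difference is an open study question. At 0.25 SD the inflation is negligible.
- A reader might conclude that the regression will adjust the association away. Its outcome and exposure are undefined, an independent-association model is a legitimate aim, and the Spearman coefficients would still be reported. A blanket ban on biomarker covariates would go too far.
- A reader might extend the point to the HLA endpoint, which opens "To investigate differences in HLA type, which has been implicated as a mechanism of viremic control in ECs". That sentence goes on to name groups and treatment arms as part of the comparison, and 13.5 states no ungrouped HLA model, so the documents do not support the extension.

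What the reply does not remove is that the stated method is a plain Spearman correlation and nothing in the plan stratifies or adjusts it. Pooled, stratified and variously adjusted analyses could all be called conforming after the data are seen.

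**Conclusion.** The point holds as a conditional weakness with a better method readily available. If the groups are pooled and both variables differ by group, the stated analysis does not hold its 5% level: about 8% at 0.5 SD, 22.5% at 0.8 SD and 44% at 1.0 SD on both. Stratifying holds it between 4.7% and 5.2% in every case simulated. If the groups are not pooled, or only one variable differs, there is no inflation. All shifts, the marker–MR correlation of 0.35 and the between-marker correlations are assumptions, because the documents give none. The overlap between the biomarkers studied and the biomarkers listed as regression factors is in the text; its effect depends on models not yet defined. This concerns one secondary objective, and the primary sCD14 analysis is untouched.

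**What to change.** In section 13.5:

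1. Make the main MR–biomarker analysis a Spearman correlation stratified by, or partial on, HIV group at baseline, and on HIV group and treatment arm for Month 12 and change data.
2. Include the same terms in the linear models, and state each model's outcome, exposure and covariates.
3. Make the main regression one biomarker of interest at a time, without other inflammatory markers. Keep any model with mutually adjusted biomarkers as a labelled supplementary analysis.

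The cost is wording and one or two degrees of freedom out of at most 80. No visits, assays or subjects are added. In the simulation the power lost when no group difference exists is about two percentage points (74% to 72% at a true r of 0.30).

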14 ETHICS/PROTECTION OF HUMAN SUBJECTS

14.1 Informed Consent Process

Informed consent is a process where information is presented to enable persons to voluntarily decide whether or not to participate as a research subject. It is an on-going conversation between the human research subject and the researchers which begins before consent is given and continues until the end of the subject's involvement in the research. Discussions about the research will provide essential information about the study and include: purpose, duration, experimental procedures, alternatives, risks and benefits. Subjects will be given the opportunity to ask questions and have them answered.

The subjects will sign the informed consent document prior to undergoing any research procedures. The subjects may withdraw consent at any time throughout the course of the trial. A copy of the informed consent document will be given to the subjects for their records. The researcher will document the signing of the consent form in the subject's medical record. The rights and welfare of the subjects will be protected by emphasizing to

them that the quality of their medical care will not be adversely affected if they decline to participate in this study. For Non-English-Speaking Participants the Investigator obtaining consent will document the consent process in the participant's electronic medical record, including the name of the interpreter. Further, all instances of use of the CC Short Written Consent Form will be reported to the IRB at the time of annual review. If the CC Short Written Consent Form is used three times or more for the same language, this will be reported to the IRB immediately, and the consent will need to be translated into that language.

14.1.1 Remote Site Consent Process

Screening may take place at either the NIH Clinical Center or the Hennepin County Medical Center (HCMC). For patients recruited from HCMC, the following consent process will be followed:

- a) The signed, witnessed, and dated consent must be completed by the Associate Investigator at Hennepin County prior to any screening labs. The original document will be maintained at the site and a copy sent to NIH.
- b) The consent will be checked for accuracy. The copy of the signed consent will be filed in the medical record.
- c) Participants recruited from HCMC will sign the NIH consent document separately upon arrival at the NIH Clinical Center and this signed consent will be filed in the medical record as well.

14.2 Subject Confidentiality

All records will be kept confidential to the extent provided by federal, state and local law. The study monitors and other authorized representatives of the Sponsor may inspect all documents and records required to be maintained by the Investigator, including but not limited to, medical records. Records will be kept locked and all computer entry and networking programs will be done with coded numbers only. Clinical information will not be released without written permission of the subject, except as necessary for monitoring by IRB, NIAID, or the Office for Human Research Protections (OHRP).

15 DATA HANDLING AND RECORD KEEPING

15.1 Data Capture and Management

Study data will be maintained in CRIMSON and collected directly from subjects during study visits and telephone calls, or will be abstracted from subjects' medical records. Source documents include all recordings of observations or notations of clinical activities and all reports and records necessary to confirm the data abstracted for this study. Source documentation (the point of initial recording of information) should support the data collected and must be signed and dated by the person recording and/or reviewing the data. Data entry into CRIMSON will be performed by authorized individuals. The Investigator is responsible for assuring that the data collected are complete, accurate, and recorded in a timely manner. Corrections to electronic data systems shall be tracked electronically (password protected) with time, date, individual making the correction, and what was changed.

15.2 Record Retention

The investigator is responsible for retaining all essential documents listed in the ICH Good Clinical Practice (GCP) Guideline. Study records will be maintained by the PI for a minimum of 3 years and in compliance with institutional, IRB, state, and federal medical records retention requirements, whichever is longest. All stored records will be kept confidential to the extent required by federal, state, and local law.

Should the investigator wish to assign the study records to another party and/or move them to another location, the investigator will provide written notification of such intent to Regulatory Compliance and Human Subjects Protection Branch (RCHSPB)/NIAID with the name of the person who will accept responsibility for the transferred records and/or their new location. Destruction or relocation of research records will not proceed without written permission from RCHSPB/NAID.

APPENDIX B: SCHEDULE OF PROCEDURES/EVALUATIONS

(After baseline, all visit windows \pm 2 weeks)

Evaluation	Screening (0 days– 2 months)	Baseline (Month 0)	Month 3	Month 6	Month 9	Month 12	Month 15
Medical/Medication History	X	X	X	X	X	X	X
Clinical Assessment	X	X	X	X	X	X	X
Physical Exam ¹	X	X	X	X	X	X	X
Carotid MRI ²		X				X	
Rectal swab & dietary questionnaire		X				X (swab only)	
Apheresis (2-Pass) ³			X			X	
CBC, differential, platelets	X	X	X	X	X	X	X
PT/PTT/D-dimer	X	X	X	X	X	X	X
Acute Care/Hepatic Panel/Mineral Panel/hsCRP/CK/Aldolase	X	X	X	X	X	X	X
Urinalysis	X	X	X	X	X	X	X
Pregnancy Testing	X	X	X	X	X	X	X
CD4/HIV-1 RNA	X	X	X	X	X	X	X
Hemoglobin A1c		X	X	X	X	X	X
Lipid Panel (fasting)	X	X	X	X	X	X	X
Hepatitis Serology	X						
ELISA/Western Blot	X ⁴						
Research Storage (Plasma, PBMC, Serum)		X	X	X	X	X	X
Research Flow Cytometry		X	X	X	X	X	X
Atorvastatin or Aspirin Dispensed			X	X	X		
Pill Count			X	X	X	X	

¹ Targeted physical exam for acute presentations following screening visit.

² Can occur any time on or between the M0 and M3 visits, based on MR availability.

³ If adequate venous access and Hg>9g/dL and PLT>50,000. If inadequate venous access, 30mL of additional blood will be drawn in lieu of apheresis (3-10mL green tops)

⁴ If not previously performed at NIH

APPENDIX C: BLOOD VOLUMES FOR SPECIMEN COLLECTION

¹ Visit	Tube Type	Screening	⁶ Baseline					End of Study
Month (M) of Study			M 0	M 3	M 6	M 9	M 12	M 15
Clinical								
CBC, differential, platelets	3mL Light lavender top	3	3	3	3	3	3	3
PT, aPTT, D-dimer, fibrinogen, protein C and S, antithrombin III	4.5 mL Light blue top	4.5	4.5	4.5	4.5	4.5	4.5	4.5
Pregnancy test: urine								
Acute Care, Hepatic and Mineral Panel	8mL Green top(lithium heparin)	8	8	8	8	8	8	8
Creatine Kinase, Aldolase, hsCRP	Same tube	X	X	X	X	X	X	X
HBsAg, anti-HBcAb, anti-HBsAb, anti-HAV IgG, HCV Ab and HCV PCR ²	8mL SST	8						
ELISA/Western Blot ³	4mL SST	4						
Lipid Panel	4 mL Green top (lithium heparin)	4	4	4	4	4	4	4
HIV-1 RNA	6mL Purple top	6	6	6	6	6	6	6
Hemoglobin A1c	3mL Light lavender top		3	3	3	3	3	3
HLA typ ³	10ml Purple top		10					
Research								
PBMC Storage ⁴	6mL Green top		55	60	60	60	60	60
Plasma Storage	6mL Dark lavender top		12	12	12	12	12	12
Serum Storage	8mL SST		8	8	8	8	8	8
Single Copy Assay	(3) 9ml Purple top		27	27			27	
Flow Cytometry	6mL Purple top	6	6	6	6	6	6	6
Daily Volume (mL)		43.5	146.5	141.5	114.5	114.5	141.5	114.5
⁴Cumulative Volume (mL)			190	331.5	446	560.5	702	816.5

¹ Visit Windows: All visit windows \pm 2 weeks after baseline

² HCV Ab will be accepted from an outside lab if performed within 2 months of of Month 0

³ Only if not previously done at NIH

⁴ An additional 30mL(3-10mL green tops) of PBMC storage will be collected if patient is unable to undergo apheresis at the designated study visits .

⁵Per NIH MEC Policy M95-9, maximum blood volumes drawn for *research purposes* for an *adult* subject (aged 18 years or older) may not exceed: 10.5 mL/kg or 550 mL, whichever is smaller, over any eight week period. Exceptions to this policy shall be approved by the IRB.

⁶ M 0 evaluations are the baseline for subsequent safety assessments. Visit must occur 0 days – 2 months after screening.

APPENDIX D: ATORVASTATIN PACKAGE INSERT

HIGHLIGHTS OF PRESCRIBING INFORMATION

These highlights do not include all the information needed to use atorvastatin calcium tablets safely and effectively. See full prescribing information for atorvastatin calcium tablets.

Atorvastatin Calcium Tablets for oral administration
 Initial U.S. Approval: 1996

RECENT MAJOR CHANGES

Dosage and Administration (2.6)	11/2012
Warnings and Precautions (5.1)	11/2012
Drug Interactions (7)	02/2012

INDICATIONS AND USAGE

Atorvastatin calcium is an inhibitor of HMG-CoA reductase (statin) indicated as an adjunct therapy to diet to:

- Reduce the risk of MI, stroke, revascularization procedures, and angina in patients without CHD, but with multiple risk factors (1.1).
- Reduce the risk of MI and stroke in patients with type 2 diabetes without CHD, but with multiple risk factors (1.1).
- Reduce the risk of non-fatal MI, fatal and non-fatal stroke, revascularization procedures, hospitalization for CHF, and angina in patients with CHD (1.1).
- Reduce elevated total-C, LDL-C, apo B, and TG levels and increase HDL-C in adult patients with primary hyperlipidemia (heterozygous familial and nonfamilial) and mixed dyslipidemia (1.2).
- Reduce elevated TG in patients with hypertriglyceridemia and primary dysbetalipoproteinemia (1.2).
- Reduce total-C and LDL-C in patients with homozygous familial hypercholesterolemia (HoFH) (1.2).
- Reduce elevated total-C, LDL-C, and apo B levels in boys and postmenarcheal girls, 10 to 17 years of age, with heterozygous familial hypercholesterolemia after failing an adequate trial of diet therapy (1.2).

Limitations of Use

Atorvastatin calcium tablets have not been studied in *Fredrickson* Types I and V dyslipidemias.

DOSAGE AND ADMINISTRATION

Dose range: 10 to 80 mg once daily (2.1).
 Recommended start dose: 10 or 20 mg once daily (2.1).
 Patients requiring large LDL-C reduction (>45%) may start at 40 mg once daily (2.1).
 Pediatric starting dose: 10 mg once daily; maximum recommended dose: 20 mg once daily (2.2).

DOSAGE FORMS AND STRENGTHS

10, 20, 40, and 80 mg tablets (3).

CONTRAINDICATIONS

Active liver disease, which may include unexplained persistent elevations in hepatic transaminase levels (4.1).
 Women who are pregnant or may become pregnant (4.3).
 Nursing mothers (4.4).
 Hypersensitivity to any component of this medication (4.2).

WARNINGS AND PRECAUTIONS

Skeletal muscle effects (e.g., myopathy and rhabdomyolysis): Risks increase when higher doses are used concomitantly with cyclosporine and strong CYP3A4 inhibitors (e.g., clarithromycin, itraconazole, HIV protease inhibitors). Predisposing factors include advanced age (> 65), uncontrolled

hypothyroidism, and renal impairment. Rare cases of rhabdomyolysis with acute renal failure secondary to myoglobinuria have been reported. Advise patients to promptly report to their physician unexplained and/or persistent muscle pain, tenderness, or weakness. Atorvastatin therapy should be discontinued if myopathy is diagnosed or suspected (5.1, 8.5).

Liver enzyme abnormalities: Persistent elevations in hepatic transaminases can occur. Check liver enzyme tests before initiating therapy and as clinically indicated thereafter (5.2).

A higher incidence of hemorrhagic stroke was seen in patients without CHD but with stroke or TIA within the previous 6 months in the atorvastatin calcium tablets 80 mg group vs. placebo (5.5).

ADVERSE REACTIONS

The most commonly reported adverse reactions (incidence ≥ 2%) in patients treated with atorvastatin calcium tablets in placebo-controlled trials regardless of causality were: nasopharyngitis, arthralgia, diarrhea, pain in extremity, and urinary tract infection (6.1).

To report SUSPECTED ADVERSE REACTIONS, contact Greenstone LLC at [name] or FDA at [name] or www.fda.gov/medwatch.

DRUG INTERACTIONS

Drug Interactions Associated with Increased Risk of Myopathy/Rhabdomyolysis (2.6, 5.1, 7, 12.3)

Interacting Agents	Prescribing Recommendations
Cyclosporine, HIV protease inhibitors (tipranavir plus ritonavir), hepatitis C protease inhibitor (telaprevir)	Avoid atorvastatin
HIV protease inhibitor (lopinavir plus ritonavir)	Use with caution and lowest dose necessary
Clarithromycin, itraconazole, HIV protease inhibitors (saquinavir plus ritonavir, darunavir plus ritonavir, fosamprenavir, fosamprenavir plus ritonavir)	Do not exceed 20 mg atorvastatin daily
HIV protease inhibitor (nelfinavir) Hepatitis C protease inhibitor (boceprevir)	Do not exceed 40 mg atorvastatin daily

- Other Lipid-Lowering Medications: Use with fibrate products or lipid-modifying doses (≥1 g/day) of niacin increases the risk of adverse skeletal muscle effects. Caution should be used when prescribing with atorvastatin calcium tablets (7).
- Digoxin: Patients should be monitored appropriately (7.8).
- Oral Contraceptives: Values for norethindrone and ethinyl estradiol may be increased (7.9).
- Rifampin should be simultaneously co-administered with atorvastatin calcium tablets (7.7).

USE IN SPECIFIC POPULATIONS

- Hepatic impairment: Plasma concentrations markedly increased in patients with chronic alcoholic liver disease (12.3).

See 17 for PATIENT COUNSELING INFORMATION

Revised: [11/2012]

FULL PRESCRIBING INFORMATION: CONTENTS*

